long-term survivor. Focal fractionated re-irradiation was used in 13 patients who were followed for a median of 30 months. Three failed with metastatic disease and the 3-year event-free (EFS) and overall survival (OS) was 71% + 14% and 67% + 16%, respectively. There were no cases of necrosis with a median combined dose of 111.6Gy localized primarily to the brainstem and cerebellum. The outcome suggested a high-rate of local control for re-irradiation with limited adverse effects. CSI was administered to 12 patients with isolated metastatic failure after metastasectomy. The median combined dose at any point of overlap with prior irradiation was 99Gy. The 3 year EFS was 53% + 20% for patients with a median follow-up of 32 months. These data suggested that some patients with extensive recurrent disease may be salvaged with CSI, provided that surgery is a component of therapy. CSI was also administered to 4 patients with a history of combined local and metastatic failure: 3 of 4 patients subsequently failed demonstrating a potential limitation to this approach in patients who have more clinically aggressive disease. In summarizing this experience, it appears that SRS should have a limited role in the treatment of recurrent ependymoma and that patients with locally recurrent EP have durable local tumor control but remain at risk for metastasis. Salvage of isolated metastatic EP failures may be possible using CSI; however, those who have combined local and metastatic failure fare poorly despite aggressive surgery and re-irradiation.

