- 5. Cardiopulmonary fitness is the ability of the cardiac and pulmonary systems to provide muscles with an adequate supply of oxygen for work. Capacity increases across childhood with age and peaks during young adulthood. Exercise capacity is typically quantified as maximal oxygen uptake (Vo2max) and is a product of maximal cardiac output (liters of blood per minute) and arterial-venous oxygen difference (milliliters of oxygen per liters of blood). Fitness levels across populations vary primarily from differences in maximal cardiac output. Therefore, this measure closely corresponds to the functional capacity of the heart [102-107].

Physical performance in children treated for recurrent ependymoma

While early research has documented the impact of changing treatment on survival [17, 108] and some late cognitive late effects [30], little work has been

> St. Jude Children's Research Hospital IRB Approval date:

IRB NUMBER: Pro00004349 IRB APPROVAL DATE: 02/01/2023

Protocol document date: 1/19/2023

Rev. 3.2 dated: 1/19/2023

done to either specifically and objectively evaluate and describe physical performance, or to look at the impact of improved surgical and radiotherapy management techniques on physical disability in this population. A longitudinal assessment of physical performance and of movement related impairments among children undergoing retreatment for ependymoma, either with focal retreatment or craniospinal irradiation after additional surgery is important as it will provide insight into the specific nature and timing of physical disability in this population. It will help assess the effectiveness of this therapy, balancing disease control against functional outcomes, including movement related morbidity in long term survivors, and provide information for targeted rehabilitation interventions designed to restore physical function, teach compensatory strategies that overcome functional loss, or adapt the environment so survivors with persistent disability can participate optimally in life roles.

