subset among a larger group of children with brain tumors, and are often evaluated only in a cross sectional, or one time point assessment. Very rarely, objective, person level function is measured. Most data comes from self- or proxy report questionnaires or from general clinician generated global scales of function. Nevertheless, there is some information in the literature describing overall brain tumor survivor outcomes that indicates that physical disability prevalence rates are potentially elevated in this population. Gains from the investigation proposed here will add to this literature. Knowledge of expected long-term clinical outcome may inform parents and clinicians during the treatment process, so they know what to expect and when and if to seek restorative rehabilitation services. This work will identify specific person and treatment related characteristics that predict poor outcomes, and potential physical impairments in this population that may be amenable to a rehabilitation type intervention.

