to the posterior fossa or occipital/parietal lobes was associated with poor outcomes. Poor physical performance was associated with not living independently and with not attending college.

Only a few authors have specifically included survivors of ependymoma in investigations, and have usually document physical ability simply as one component of global clinical outcome [116]. At least one investigation has been longitudinal, but did not include children with recurrent disease [18]. Benesch et al [116] included 6 children with ependymoma when they developed the LESS scoring system for clinicians to use when quantifying late effects in children after radiation and chemotherapy for brain tumor. Neurological, endocrine, visual/auditory and an "other" category are included on this severity rating scale. Children with higher scores on this rating scale had lower quality of life scores than did those with lower scores, indicating an association between neurological outcome and overall quality of life. Morris et al [18] evaluated neurological morbidity in 96 children with ependymoma within 3 months of conformal cranial irradiation and every 6-12 months thereafter until 120 months post radiation. Assessments were performed by a neurologist and included a four point grading of multiple neurologic outcomes including muscle strength and strength, motor control, coordination and gait. Neurologic impairments were most prevalent at baseline and decreased over time. However, at 60 months post treatment, participants still had an average of 2.2 neurological deficits. There were 17 patients with at least one severely compromised function 60 months post therapy.

We could identify only one study among children with recurrent ependymoma who treated with re-irradiation that very briefly described performance type outcomes. Liu et al, [108] in a study designed to evaluate the curative impact of hypofractionated re-irradiation in 6 children with local recurrence of ependymoma, reported that 3 children had imaging changes consistent with necrosis 7-8 months after treatment. Among these 3 children, 1 had no physical symptoms, 1 had ataxia that resolved, and 1 had headache related pain treated with over the counter medication.

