# 11.4 Statistical Analysis of Secondary Objective 1.2.3 Physical Performance

Objective: To describe physical performance and movement in children, adolescents and young adults with ependymoma treated with a second course of radiation.

Physical performance measures will be obtained at baseline, 12, 24, 36, 48 and 60 months. We will provide descriptive statistics of the following outcomes at each time point, and also provide the plots of individual profiles and mean profiles of the outcomes across time. The descriptive statistical analysis will be stratified by gender, age at diagnosis and total dose of brain radiation.

To model the outcomes' pattern and change over time, we will use generalized estimating equation (GEE) methodology with time as the main independent variable while adjusting for gender, age at diagnosis and total dose of brain radiation, including an interaction term if indicated. The assigned distribution and link function in each model will depend on the characteristic of the specific outcome as listed in next paragraph(s). The continuous measures will be modeled using normal distribution and identity link whereas the binary outcomes will be modeled using binomial distribution and logit link.

These analyses will be conducted at the conclusion of the trial and at an interim time point at which we have 15 patients in each stratum (a total of at least 45 patients) followed for 1 year. The results of the interim analyses will be submitted for presentation at an appropriate national scientific meeting, as well as to the CT-SRC.

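### Section 2.5 promises treatment-related predictors of poor physical outcome, but the section 11.4 model and tables contain no focal/craniospinal or tumour-location term, and the one dose covariate is undefined

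*Combined protocol and SAP*

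**What the plan says.** Section 2.5 describes a population retreated "either with focal retreatment or craniospinal irradiation after additional surgery" and commits to finding predictors: "This work will identify specific person and treatment related characteristics that predict poor outcomes". Its own literature summary gives a location signal. In an earlier survivor cohort, radiation "to the posterior fossa or occipital/parietal lobes was associated with poor outcomes". Objective 1.2.3 in section 1.2 speaks of exploring differences in physical performance, and the hypothesis above it links side effects to treatment parameters, including dose to normal tissue volumes. Section 2.1 says side effects among the sponsor's re-irradiated patients have been greatest after craniospinal treatment.

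Section 11.4 restates the objective more narrowly: "To describe physical performance and movement in children, adolescents and young adults with ependymoma treated with a second course of radiation". Time is the main regressor in the GEE, fitted "while adjusting for gender, age at diagnosis and total dose of brain radiation, including an interaction term if indicated". The descriptive tables are split by the same three variables. Treatment stratum appears only in the trigger for the interim analysis (15 patients per stratum followed for one year).

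The neighbouring sections differ. Section 11.2 acknowledges that focal and craniospinal treatment are not randomly assigned and plans an adjusted comparison. Section 11.3 stratifies by the two treatments and compares them over time.

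**The concern.** A model can only identify predictors that are in it. The treatment characteristics that the protocol itself treats as important for function are the irradiated volume (focal or craniospinal) and the location. Neither enters the 11.4 model or tables. The only treatment variable is a brain dose, and it cannot stand in for volume. Craniospinal treatment also covers the spinal subarachnoid space (section 5.7.2), which a brain-dose covariate cannot register under any definition.

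Two things are at stake. The measured performance battery (motor proficiency, balance, strength, fitness) would be reported without showing whether outcomes differ between the two treatments. And anyone who reads the dose coefficient would read a quantity that mixes dose with volume, in a direction that depends on a definition the plan does not give.

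**Working it through.** Section 11.4 states no sample size, power or effect size, so there is no figure to reproduce. The check has three parts.

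**1. Promise against model**

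| Factor | Raised in | In 11.4 model or tables? | In sister sections? |
|---|---|---|---|
| Focal vs craniospinal | 2.1, 2.5 | No | Yes: 11.2, 11.3 |
| Location | 2.5 | No | Not named as a term |
| Brain dose | 11.4 | Yes, undefined | Not applicable |

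**2. Does dose track volume?** Craniospinal-minus-focal difference under each plausible meaning of total brain dose:

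- Neuraxis prescription (section 5.2: 36 to 39.6 Gy, against 54 Gy for most focal cases): 36 - 54 = -18 Gy; 39.6 - 54 = -14.4 Gy. Opposite to volume.
- Combined dose over both courses (section 2.1): focal patients were treated "with a median combined dose of 111.6Gy localized primarily to the brainstem and cerebellum"; for craniospinal patients, "The median combined dose at any point of overlap with prior irradiation was 99Gy". 99 - 111.6 = -12.6 Gy. Opposite to volume, but the groups are retrospective (13 focal patients; 12 with isolated metastatic failure), and the 99 Gy is a dose at points of overlap, not a total brain dose.
- Second-course maximum including boost (50.4 to 59.4 Gy, against 54 Gy): -3.6 to +5.4 Gy. No fixed direction.
- Second-course mean brain dose. Assumption: focal treatment covers 5% to 50% of the brain at 54 Gy and nothing elsewhere, so 2.7 to 27 Gy, against a nominal 36 Gy: +9 to +33.3 Gy. Same direction as volume.

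**3. What omission does to the dose slope.** Let bD be the true dose slope, bV the true craniospinal effect, p the craniospinal share, d the dose difference and s the within-group dose SD. Without a treatment term,

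fitted slope = bD + bV × k, where k = d·p(1-p) / [s² + d²·p(1-p)].

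From Table 11.0, p = (7 + 16 + 5)/50 = 0.56, so p(1-p) = 0.2464. The documents do not give s, bD or bV; the values below are assumptions.

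With d = -12.6 and s = 6: k = -3.105/(36 + 39.12) = -0.0413. The sign then reverses only if the craniospinal effect exceeds the effect of 1/0.0413 = 24.2 Gy of dose. The same threshold is 15.5 Gy at s = 3, 44.8 Gy at s = 10 and 85.1 Gy at s = 15.

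GEE simulations (90 patients, 6 visits, 200 runs, bD = -0.020 SD per Gy):

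| d (Gy) | s (Gy) | bV (SD) | Mean slope without treatment term | Mean slope with it |
|---|---|---|---|---|
| -12.6 | 6 | -0.5 | +0.001 | -0.019 |
| -12.6 | 6 | -0.2 | -0.012 | -0.020 |
| -12.6 | 10 | -0.5 | -0.009 | -0.020 |
| 0 | 6 | -0.5 | -0.019 | -0.019 |
| +5.4 | 6 | -0.5 | -0.038 | -0.022 |

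In the first row the slope had the wrong sign in 56% of runs without the term and 7% with it. Across rows the dose effect is erased, attenuated, unaffected or exaggerated, depending on inputs the plan does not give. Adding treatment group brings the mean back to about -0.02 each time. Location was not simulated, because the documents give no figures for it.

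**The case against.** The strongest defence is that 11.4 is descriptive. Its stated objective is to describe, time is the main regressor, and dose is an adjustment covariate that nothing says will be reported as a treatment effect. That stands against any claim that 11.4 will publish a misleading dose effect. It does not answer the main point, because tables not split by treatment cannot describe a difference between treatments, and section 2.5 promises predictors.

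Second, the mention of focal and craniospinal retreatment in 2.5 describes who is studied; the balance named there is disease control against function, not one treatment against the other. That is a fair reading. The promise of treatment-related predictors is separate and explicit.

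Third, the contrast is partly covered elsewhere. Section 11.2 compares neurological severity, including ataxia, between treatment groups, and 11.3 compares the PedsQL Brain Tumor Module, which has a movement and balance scale. This narrows the gap, but the measured performance battery remains uncovered.

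A reader might infer from the 99 and 111.6 Gy medians that total dose runs opposite to volume and that the dose effect will change sign. The documents do not support this: the variable is undefined, the 99 Gy is an overlap dose in a small group, and reversal needs a large craniospinal effect that no passage supplies. A reader might also want age at diagnosis replaced by age at re-irradiation. The risk-factor list in section 2.3 that names age at treatment concerns cognition, and section 2.9 lists both ages as host factors, so that swap is a preference.

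**Conclusion.** The mismatch between 2.5 and 11.4 is real and rests on the text alone. Followed as written, 11.4 cannot show whether measured physical performance differs by focal versus craniospinal treatment or by tumour location. Its dose coefficient is open to confounding by volume if craniospinal treatment affects function and mean dose differs between groups. The direction is opposite to volume for neuraxis prescription, undetermined for boosted maximum and the same as volume for mean brain dose (under the brain-coverage assumption above). No single magnitude can be given, and sign reversal is possible but not established. This affects one secondary objective, not the primary analysis; it is worth correcting because the correction is cheap and the sister sections already make the comparison.

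**What to change.** In section 11.4:

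- Add focal versus craniospinal treatment, with a treatment-by-time term, and tumour location (infratentorial versus supratentorial) to the GEE and to the descriptive strata.
- Define the dose variable: which course or courses, and whether prescription, maximum or mean.
- Interpret dose only with treatment group in the model.
- State that the focal/craniospinal contrast is exploratory and non-randomised, as 11.2 already recognises.

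The cost is analysis-plan wording. Treatment group is core trial data, and section 4.2 lists tumour location among the factors to be monitored. The downside is a few more parameters in at most about 90 patients, fewer at later visits because disease progression is an off-study criterion (section 8.1). The two-level location split is also coarse: it isolates the posterior fossa but not the occipital or parietal lobes.

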#### 2.6 Neuroimaging

Patterns of recurrence of ependymoma have been little studied in the literature, but may provide valuable information regarding efficacy of initial radiotherapeutic target volumes. It would be expected that, given the history of prior focal RT, the pattern of recurrent disease would differ from that typically seen at initial presentation. Initial, pre-treatment conventional imaging and post-recurrence conventional MR imaging will be analyzed for spatial distribution of disease, compared to each other and compared to initial radiation dosimetry maps to evaluate how the disease pattern is altered in the post-irradiation brain.

Evidence of tissue damage, including atrophy and encephalomalacia, has been observed in untreated brain in initially successfully treated patients who, though initially without clinical evidence of function loss, subsequently experienced complications. By assessing alterations in structural, microstructural and physiologic properties of both treated and untreated brain tissue over time and comparing to dose distribution and measures of cognition and function over time, imaging-based biomarkers predictive of treatment-related functional or cognitive compromise may be established. Evaluation of response of primary site and metastatic disease to radiation therapy will be assessed using quantitative MR imaging and PET.

#### 2.6.1 Magnetization-Transfer Imaging

As early damage to brain tissue can appear deceptively normal on conventional anatomic MR images [117], reliance on visual inspection may be insufficient to appreciate the true extent of microstructural damage. Diffusion tensor imaging has proved effective in delineating white matter tracts, and has demonstrated changes in fractional anisotropy (FA) and other diffusion parameters in normal-appearing white matter following radiation therapy above a certain threshold dose [118]. These changes in water diffusivity have been shown to correlate with damage to structural components of the white matter tracts [119].

Magnetization-transfer (MT) MR techniques offer an alternative approach toward evaluation of brain tissue integrity, via evaluation of macromolecular content. In this technique, the protons of MR-invisible macromolecules are saturated by manipulation of the radiofrequency (RF) pulse [120]. These protons then exchange their saturation by various mechanisms with the water peak. This results in a decrease in the detectable water signal, serving as an indirect marker of the size of the macromolecular "pool". Because in white matter this pool is presumed to be largely due to myelin, changes in the magnetization-transfer ratio (MTR, 1-

IRB Approval date:

Rev. 3.2 dated: 1/19/2023 Protocol document date: 1/19/2023 St. Jude Children's Research Hospital

IRB NUMBER: Pro00004349

Ssat/So) are felt to be representative in changes in myelination. Indeed, changes in magnetization-transfer ratio have been shown to correlate to white matter damage and recovery in multiple sclerosis and other white matter disorders [121, 122]. Changes in MTR in normal-appearing white matter (NAWM) have been found to precede the development of lesions in multiple sclerosis (MS); changes in MTR in normal-appearing gray matter [123] may have an even stronger correlation with clinical course [124, 125]. There is a strong possibility that, as in MS, invisible gray matter alterations may be a more sensitive predictor of clinical course following radiation injury. Though MT imaging has the potential to detect these changes in both gray matter and white matter prior to manifestation on standard MR sequences, there is a dearth of studies of MT in this setting, likely due to the historically long image acquisition time (~12 minutes for MT sensitized and non-MT sensitized sequences) limiting routine utilization [117]. However, this limitation has been overcome by the recent development of bSSFP –based MT techniques requiring on the order of 3.5 minutes total acquisition time, quite feasible for inclusion in a routine imaging protocol [120, 126].

Magnetization-transfer imaging with bSSFP technique in this protocol will serve three purposes: 1) comparison to DTI regarding sensitivity for radiation-induced white matter changes, 2) assessment of early cortical gray matter damage, not possible with DTI, and 3) comparison of gray matter and white matter damage. In addition, information derived from MT imaging will be complementary to DTI, as the former relies primarily on neuronal density and the latter on directionality [127]. FMRIB Software Library (FSL) [128] will be utilized for segmentation of gray matter from white matter for analysis of MT data, which will then be correlated with radiation field maps, perfusion and DTI data. Comparison will also be made to grading of gray and white matter damage on conventional imaging.

#### 2.6.2 Diffusion-Tensor Imaging (DTI)

DTI is the most important magnetic resonance imaging technique to investigate brain white matter development and injury in vivo. Numerous lines of evidence support the use of DTI in studying treatment effects on brain structures composed predominantly of white matter tracts [129-132]. Animal histological studies demonstrated strong correlation between changes in DTI metrics and radiation-induced demyelination, axonal degeneration, and necrosis in the brain [119]. DTI metrics were also found to be significantly related to neurological deficits in patients [133-136]. Brainstem and cerebellar white matter pathways will be studied with DTI in this protocol due to their proximity to posterior fossa tumors and susceptibility to radiation injury. When craniospinal irradiation is delivered for patients with distant metastasis, supratentorial white matter tracts are likely to be affected and will be studied as well.

For ependymoma recurrent in the posterior fossa, white matter tracts in the brainstem and cerebellum are particularly vulnerable to therapy-induced injury.

IRB Approval date: St. Jude Children's Research Hospital

IRB NUMBER: Pro00004349

Protocol document date: 1/19/2023

Rev. 3.2 dated: 1/19/2023

Radiation dose delivered to these critical organs from previous radiation treatments often reach their tolerance estimated to be in the range of 54-60Gy [137]. Severe motor and sensory deficits could occur if irradiated fiber tracts have not been repaired sufficiently from prior irradiation at the time of second irradiation. We will perform baseline DTI studies prior to re-irradiation to evaluate the recovery status of brainstem and cerebellum white matter tracts. The results will be compared to age-related benchmark values previously obtained from healthy volunteer children. Serial DTI studies will also be performed at each follow-up visit to monitor the evolution of therapy-induced injury and recovery in white matter structural integrity.

For recurrent brain tumors, DTI can be helpful in assessing the tumor infiltration into the peritumoral white matter regions [138, 139]. DTI has also been used to differentiate recurrent brain tumors from radiation injury [140]. These potentials will be explored in this unique pediatric population. For normal tissue protection, changes in normal white matters adjacent to tumor or tumor bed due to surgical resection and reirradiation in children were rarely documented. Long term effects of re-irradiation on cerebral white matter development in children were not clearly understood. Serial DTI studies performed in this trial will be analyzed to answer above questions for reducing the knowledge gap. Collected DTI data will help estimate the radiation tolerance of cerebral white matters and the brain in children.

DTI will be acquired with a double spin echo EPI pulse sequence which applies diffusion-encoding gradients along 12 non-linear, non-coplanar directions in space. To facilitate comparisons with magnetization transfer imaging and previously acquired benchmark data in healthy children, examinations will be preferentially performed at 3T but may be performed at 1.5T if imaging at 3T is contraindicated. Each DTI study will contain 4 repetitions of the same diffusion pulse sequence to improve signal to noise ratio. These 4 imaging datasets will be spatially registered to a raw image dataset without diffusion gradient encoding (b=0) to correct for patient motion and linear system drift during acquisition before performing diffusion tensor calculation. Voxel-based DTI metrics which can be calculated for quantitative analysis include apparent diffusion coefficient (ADC), fractional anisotropy (FA), relative anisotropy (RA), parallel and perpendicular eigenvalues ( $\lambda_{//}$  and  $\lambda_{\perp}$ ). ADC and FA values represent the magnitude and directionality of water diffusion in each tissue voxel, respectively. ADC has the unit of mm^2/s. FA is dimensionless and ranges from 0 (isotropic diffusion) to 1 (highly directional). To determine if DTI reflects and predicts treatment toxicity, changes in these imaging metrics from serial DTI measurements will be correlated with results of longitudinal neurological outcomes and radiation dosimetry.

